For the purpose of dose escalation, we will require a 28 day observation period from the time the last patient in a given cohort was treated. For the purpose of calculating the MTD, we will require a minimum of 28 days of observation for each patient.

Dose escalation in Phase 1 will proceed as follows:

If none of the first 3 evaluable patients in a dose cohort experience a DLT in the first two cycles, then the next 3 patients will be treated at the next higher dose cohort. If 1 of 3 patients within a cohort experiences a DLT in the first two cycles, then 3 additional patients will be added to that cohort. If a second patient experiences a DLT at that dose level in the first two cycles, the next cohort will not be initiated, and the dose of one or more drugs will be de-escalated. Patients at each dose level will be evaluated for at least 28 days from the start of treatment before additional patients can be treated at a higher dose level. If DLTs are observed in 2 or more patients within a cohort, the maximum tolerated dose (MTD) will have been exceeded and no further patients will be treated at that dose level.

DLT evaluation and enrollment decisions will follow the guidance in Table 3.

Table 3: Algorithm for Dose-Escalation Decisions

Number of Patients with DLT at a Given Dose Level	Dose Escalation Decision Rule
0/3	Escalation will occur into the next highest dose cohort
1/3	Enroll 3 additional patients at current dose level
$\geq 2/3$	Stop enrollment. Enroll 3 more patients at the lower dose level, if only 3 were previously entered, or at an intermediate dose level.
1/6	Open next cohort
$\geq 2/6$	Stop enrollment. Enter 3 more patients at the lower dose level at an intermediate dose level.

Dose escalation will continue until either the MTD or maximum planned dose of APX005M is reached, with a minimum of 3 patients enrolled in each cohort.

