The MTD is defined as the highest dose associated with DLTs in less than or equal to 33% of patients receiving APX005M in combination with cabiralizumab or with cabiralizumab and nivolumab, administered during the DLT period. This will normally be the dose recommended for further study; however, based on review of safety, PK, and PD (if available) data, the RP2D could be lower than the MTD. If the MTD is not reached, and the highest evaluated APX005M dose in combination with cabiralizumab and nivolumab is well tolerated, the data will be reviewed to assess whether further dose escalations of APX005M are warranted.

In order to calculate the MTD and RP2D, every patient included in this calculation must have received at least 2 doses of study drugs and have been monitored for at least 2 full cycles (28 days). If a patient does not receive 2 doses of study drugs and does not complete safety assessments (e.g., safety lab and/or AE reporting) in the first 28 days for reasons other than drug-

related AEs (e.g., disease progression or withdrawal of consent), then an additional patient will be enrolled into the cohort so that the cohort has at least 3 patients evaluable for 28 days. All such discussions and decisions will be documented as part of the dose escalation decision-making process.

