3.1.2.1.1 Dose Limiting Toxicity

A DLT is defined as any of the following AE (graded using National Cancer Institute [NCI] Common Terminology Criteria for Adverse Events [CTCAE] v5.0), which occurs during the first 28-days of cabiralizumab/APX005M or nivolumab/cabiralizumab/APX005M administration that is not clearly due to a cause other than the study medication (e.g., disease under study, car accident).

1. Grade 4 neutropenia or grade 4 thrombocytopenia lasting ≥ 7 days
2. Neutropenic fever of any duration
3. Grade ≥ 3 thrombocytopenia if associated with:
 - a. Clinically significant bleeding or requirement for platelet transfusion, or
 - b. A life-threatening bleeding event which results in urgent intervention and admission to an Intensive Care Unit
4. Any grade ≥ 3 non-hematologic toxicity (not laboratory) **with the exception of:**
 - Grade 3 tumor flare (defined as local pain, irritation, or rash localized at sites of known or suspected tumor)
 - Grade 3 joint pain
 - Grade 3 fatigue lasting less than 1 week
 - Serum elevations of CK $> 15X$ ULN and $\leq 20X$ ULN that last for < 7 days
 - Grade 3 or Grade 4 electrolyte abnormalities that are not complicated by associated clinical adverse experiences, last less than 72 hours and either resolve spontaneously or respond to conventional medical intervention
 - Grade 3 nausea, vomiting, or diarrhea lasting less than 72 hours, and either resolves spontaneously or responds to conventional medical intervention including adequate anti-emetics or other supportive care
 - Grade 3 or grade 4 elevation of amylase or lipase not associated with clinical or radiographic evidence of pancreatitis
 - Grade 3 fever not associated with hemodynamic compromise (eg, hypotension, clinical or laboratory evidence of impaired end-organ perfusion)
 - Grade 3 endocrinopathy that is well controlled by hormone replacement
 - Grade 3 infusion reaction that returns to Grade 1 in < 6 hours
5. Any Grade ≥ 3 non-hematologic laboratory value if:
 - a. Immune suppression other than corticosteroids is required to treat the subject, or
 - b. The abnormality itself solely leads to hospitalization, or
 - c. The abnormality persists for > 1 week. For AST/ALT $> 12X$ ULN, DLT is defined as not improving after > 7 days or the value increases by more than $5X$ ULN over 72 hours;

e.g. if an AST of 300 rises to 500 in 72 hours, where AST 36 is ULN, a rise of 200 is greater than 5X ULN (180) and would be considered a DLT

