6. Any Grade ≥ 3 AST/ALT elevation combined with total bilirubin $>2x$ ULN (for patients with Gilbert's syndrome, use bilirubin $\geq 2X$ baseline) or INR > 1.5 not on warfarin
7. Failure to recover from a treatment-related AE to baseline or \leq Grade 1 within 12 weeks of last dose of investigational product (except Grade 2 alopecia and Grade 2 fatigue)
8. Any death not clearly due to the underlying malignancy or extraneous causes (e.g. car accident)
9. Recurrence of Grade 4 rash, or other Grade 3 immune-related AE (irAE), or Grade 4 infusion-related AE. Recurrent grade 3 infusion reactions should be discussed with the study PI.
10. Any toxicity requiring dose reduction of APX005M or permanent discontinuation of any of the study drugs.

irAE is defined as a clinically significant AE that is associated with study drug exposure, with the exception of AEs related to cytokine release, attributable to APX005M, and is consistent with an immune-mediated mechanism.

Certain toxicities, even if already resolved, will make it unacceptable to advance to subsequent cohorts as planned, including but not limited to:

- Grade 4 myocarditis; Grade 3 myocarditis will need to be discussed with the study PI
- Grade 3 neurotoxicity with the exception of peripheral neuropathy
- Grade 4 pneumonitis
- Bone marrow aplasia

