4.3 Method of Assigning Patient Identification

Patients must be able to provide written informed consent and meet all eligibility criteria. No waivers of inclusion or exclusion criteria will be granted by Sponsor or its designee for any patient enrolled in the study. Before enrolling a patient, all eligibility criteria must be satisfied.

See Section 4.4.1 and Figure 6 for dosing schema. Patients who qualify for Phase 1 dose escalation of the study will be enrolled as follows:

- Cohort 1 will be enrolled first and these patients will be followed one 14-day cycle.
- Once the DLT follow-up period of 28 days is cleared for Cohort 1, simultaneous enrollment to Cohort 2 and Cohort 3 will occur. Patients in these cohorts will be treated for a total of one 14-day cycle.
- Simultaneous enrollment into Cohort 4 and Cohort 5 will proceed once the 14-day DLT

period for dose escalation is cleared in the preceeding Cohorts 2 and 3.

- Once the DLT period of 28 days for dose escalation is cleared Cohorts 4 and 5, enrollment to the final Cohort 6 will occur.
- The MTD will be calculated for patients who have received at least 2 cycles (at least 28 days) of study drug.
- Dose escalation into sequential dose levels of APX005M in combination with cabiralizumab and nivolumab may proceed until DLTs are observed either in the cabiralizumab/APX005M doublet therapy cohorts 1, 3, and 5 or in the nivolumab/cabiralizumab/APX005M triplet therapy cohorts after discussion and agreement between the PIs and Industry Collaborators.

In Phase 1b, a maximum of 34 patients will be enrolled per disease-specific cohort (advanced melanoma, NSCLC, or RCC). Enrollment will be open for all cohorts in parallel and will continue until the enrollment target is reached. Once a disease cohort is filled, further enrollment will be restricted to the cohort(s) that have not been filled. A total of approximately 102 patients will be enrolled in the Phase 1b arm of the study.

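### The MTD/RP2D calculation admits only patients with two doses and 28 days of monitoring, and makes no exception for a patient whose DLT prevents either

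*Combined protocol and SAP*

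**What the plan says.** Two places restrict who enters the calculation. Section 3.1.2.1 says that, for the MTD and RP2D, "every patient included in this calculation must have received at least 2 doses of study drugs" and have been followed for two full cycles (28 days). Section 4.3 says "The MTD will be calculated for patients who have received at least 2 cycles (at least 28 days) of study drug". Neither sentence mentions DLTs.

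Earlier in Section 3.1.2.1 only the observation requirement appears, without a number of doses: "For the purpose of calculating the MTD, we will require a minimum of 28 days of observation for each patient".

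The rules that use DLTs have no dose minimum:

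- Section 3.1.2.1.1 defines a DLT as a listed event "which occurs during the first 28-days of cabiralizumab/APX005M or nivolumab/cabiralizumab/APX005M administration".
- Section 3.1.2.1 states: "If DLTs are observed in 2 or more patients within a cohort, the maximum tolerated dose (MTD) will have been exceeded". Table 3 agrees.
- The same section sets the threshold: "The MTD is defined as the highest dose associated with DLTs in less than or equal to 33% of patients receiving APX005M".

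The 0/3 escalation rule in Section 3.1.2.1 refers to the first three *evaluable* patients but does not define the word there.

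Section 3.1.2.1 also has a replacement clause. If a patient misses the minimum for a reason other than a drug-related AE, "an additional patient will be enrolled into the cohort so that the cohort has at least 3 patients evaluable for 28 days".

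**The concern.** A 3+3 design normally counts a patient from the moment a DLT occurs, and requires full exposure and follow-up only of patients who are to be counted as free of DLT. Here the minimum is written for every patient in the calculation. The patients it removes are those whose toxicity came early and was severe enough to end treatment, which is the information the calculation exists to capture.

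At stake is the consistency of a primary phase 1 result. The RP2D is a primary objective (Section 2.1.1), and Section 7.1 says that the three phase 1b cohorts proceed using the MTD. If two sections select different patients, the same data can support two different statements about one dose level.

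**Working it through.** **Step 1: can a patient have a DLT and miss the minimum?** Cycles last 14 days and drugs are given on Day 1, so dose 2 falls on day 15 of a 28-day DLT window. The plan gives two routes.

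- Table 5 (Section 4.9) stops all three drugs for a grade 4 infusion reaction to any of them, and for grade 4 pneumonitis or creatinine elevation. Item 10 of Section 3.1.2.1.1 makes a toxicity that permanently stops any study drug a DLT. If this happens after dose 1, there is no dose 2. Section 3.1.3 brings the patient back 28 (±7) days after the last dose, so follow-up to day 28 is possible and the dose minimum alone excludes the patient.
- Item 8 lists "Any death not clearly due to the underlying malignancy or extraneous causes". A patient who dies in this way before day 28 cannot meet the 28-day minimum, whatever the number of doses.

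Not every early DLT is affected. A patient who stops one drug while another continues (Section 4.6), or who skips only cycle 2 (Section 4.7), may still qualify.

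**Step 2: is such a patient replaced?** No. The replacement clause covers reasons other than drug-related AEs. Read literally, a patient stopped by a drug-related DLT is neither counted nor replaced.

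**Step 3: effect on the observed rate.** Let n be the patients treated in a cohort, d those with a DLT, k the DLT patients who miss the minimum, and m the patients without a DLT who miss it. With no replacement:

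rate = (d − k) / (n − k − m)

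| Observed | k | m | Rate in the restricted calculation |
|---|---|---|---|
| 3/6 = 50.0% | 1 | 0 | 2/5 = 40.0% |
| 3/6 | 2 | 0 | 1/4 = 25.0% |
| 3/6 | 3 | 0 | 0/3 = 0% |
| 3/6 | 0 | 1 | 3/5 = 60.0% |
| 3/6 | 1 | 1 | 2/4 = 50.0% |
| 2/6 = 33.3% | 1 | 0 | 1/5 = 20.0% |
| 2/6 | 2 | 0 | 0/4 = 0% |
| 2/6 | 0 | 1 | 2/5 = 40.0% |

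**Step 4: compare with the two rules.** A 3/6 cohort (one DLT in the first three patients, two in the next three) exceeds the MTD under the rule for two or more DLTs. Under the restricted calculation it satisfies the 33% definition when k = 2 or 3 and m = 0, but not when k = 1. The 2/6 rows are less clear, because 33.3% may already meet the definition if 33% stands for one third. Leaving out a patient without a DLT moves the rate upwards, so the net direction is not fixed.

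Table 3 has rows only for three and six patients, so the reduced denominators bear on the 33% calculation and not on Table 3.

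**The case against.** The strongest reply is that the rule for two or more DLTs is mandatory and has no dose minimum. A 3/6 cohort is closed whatever fraction is computed later. This stands. A reader might infer that the restriction lets a toxic cohort be passed, or that it raises the chance of escalation by some percentage. The documents do not support that: Table 3 and the closing rule still act on early DLTs, and any escalation probability would need a true DLT rate and a share of DLTs before dose 2, neither of which is given.

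Second, the intent seems clear. The MTD definition speaks of patients receiving APX005M, and declining to replace patients lost to drug-related AEs makes sense only if they stay in the count. This is probably right as to intent, so it would be too strong to say that the plan means to discard early DLTs. But the clause governs replacement only, and the sentence that governs inclusion has no exception. Section 7.1 does not settle it: it refers back to the 3+3 description, where both rules stand.

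Third, the example is narrow. At least two of three DLT patients must miss the minimum, and grade 4 pneumonitis already bars advancement under Section 3.1.2.1.1. Section 4.3 is an enrolment summary rather than the MTD definition. All of this is fair and limits the size of the point.

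Fourth, a reader might infer from Section 7.1 that up to 102 phase 1b patients would be treated at a wrongly derived MTD. The synopsis and Sections 3.1, 3.1.2.3 and 4.4.1 treat them at the RP2D. Section 3.1.2.1 allows the RP2D to be below the MTD and requires a safety teleconference before each new dose level. These safeguards reduce the risk, but none says who is counted.

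**Conclusion.** The point holds as a contradiction about who enters the MTD/RP2D calculation. The same 3/6 cohort is above the MTD under one rule and 1/4 (25%), within the 33% definition, under another if two of the three DLT patients had one dose. No section says which prevails. The *evaluable* qualifier in the 0/3 rule adds to the uncertainty, because it could be read with or without the two-dose minimum.

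The conclusion rests on the literal text and on the absence of replacement for drug-related AEs; it assumes no DLT rate. The practical size is unknown and is limited by the cohort-closing rule and the safety review. It should still be corrected, because it concerns a stated rule for a primary result and the remedy is short.

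**What to change.** Reconcile Sections 3.1.2.1 and 4.3 through one DLT-evaluable definition, used for Table 3 (including the word *evaluable* in the 0/3 rule), the MTD and the RP2D, and carry it into the synopsis. Suggested content:

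- A patient with a protocol-defined DLT in the 28-day window is counted, whatever the number of doses received or the length of follow-up.
- The two-dose and 28-day minimum applies only to patients without a DLT.
- State whether a patient without a DLT who misses the minimum because of a drug-related AE, for example by skipping cycle 2 under Section 4.7, is replaced. At present that patient too is neither counted nor replaced.

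The first two items change wording only and need no extra patients or procedures. The third could add a patient if replacement is chosen. The one downside is that the reported DLT rate may be slightly less favourable. No dose or treatment rule changes.

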3.1.2.1.1 Dose Limiting Toxicity

A DLT is defined as any of the following AE (graded using National Cancer Institute [NCI] Common Terminology Criteria for Adverse Events [CTCAE] v5.0), which occurs during the first 28-days of cabiralizumab/APX005M or nivolumab/cabiralizumab/APX005M administration that is not clearly due to a cause other than the study medication (e.g., disease under study, car accident).

1. Grade 4 neutropenia or grade 4 thrombocytopenia lasting ≥ 7 days
2. Neutropenic fever of any duration
3. Grade ≥ 3 thrombocytopenia if associated with:
 - a. Clinically significant bleeding or requirement for platelet transfusion, or
 - b. A life-threatening bleeding event which results in urgent intervention and admission to an Intensive Care Unit
4. Any grade ≥ 3 non-hematologic toxicity (not laboratory) **with the exception of:**
 - Grade 3 tumor flare (defined as local pain, irritation, or rash localized at sites of known or suspected tumor)
 - Grade 3 joint pain
 - Grade 3 fatigue lasting less than 1 week
 - Serum elevations of CK $> 15X$ ULN and $\leq 20X$ ULN that last for < 7 days
 - Grade 3 or Grade 4 electrolyte abnormalities that are not complicated by associated clinical adverse experiences, last less than 72 hours and either resolve spontaneously or respond to conventional medical intervention
 - Grade 3 nausea, vomiting, or diarrhea lasting less than 72 hours, and either resolves spontaneously or responds to conventional medical intervention including adequate anti-emetics or other supportive care
 - Grade 3 or grade 4 elevation of amylase or lipase not associated with clinical or radiographic evidence of pancreatitis
 - Grade 3 fever not associated with hemodynamic compromise (eg, hypotension, clinical or laboratory evidence of impaired end-organ perfusion)
 - Grade 3 endocrinopathy that is well controlled by hormone replacement
 - Grade 3 infusion reaction that returns to Grade 1 in < 6 hours
5. Any Grade ≥ 3 non-hematologic laboratory value if:
 - a. Immune suppression other than corticosteroids is required to treat the subject, or
 - b. The abnormality itself solely leads to hospitalization, or
 - c. The abnormality persists for > 1 week. For AST/ALT $> 12X$ ULN, DLT is defined as not improving after > 7 days or the value increases by more than $5X$ ULN over 72 hours;

e.g. if an AST of 300 rises to 500 in 72 hours, where AST 36 is ULN, a rise of 200 is greater than 5X ULN (180) and would be considered a DLT

6. Any Grade ≥ 3 AST/ALT elevation combined with total bilirubin $>2x$ ULN (for patients with Gilbert's syndrome, use bilirubin $\geq 2X$ baseline) or INR > 1.5 not on warfarin
7. Failure to recover from a treatment-related AE to baseline or \leq Grade 1 within 12 weeks of last dose of investigational product (except Grade 2 alopecia and Grade 2 fatigue)
8. Any death not clearly due to the underlying malignancy or extraneous causes (e.g. car accident)
9. Recurrence of Grade 4 rash, or other Grade 3 immune-related AE (irAE), or Grade 4 infusion-related AE. Recurrent grade 3 infusion reactions should be discussed with the study PI.
10. Any toxicity requiring dose reduction of APX005M or permanent discontinuation of any of the study drugs.

irAE is defined as a clinically significant AE that is associated with study drug exposure, with the exception of AEs related to cytokine release, attributable to APX005M, and is consistent with an immune-mediated mechanism.

Certain toxicities, even if already resolved, will make it unacceptable to advance to subsequent cohorts as planned, including but not limited to:

- Grade 4 myocarditis; Grade 3 myocarditis will need to be discussed with the study PI
- Grade 3 neurotoxicity with the exception of peripheral neuropathy
- Grade 4 pneumonitis
- Bone marrow aplasia

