1.4.1 Serum Enzyme Elevations with Cabiralizumab

In Study FPA008-003, 34 subjects have been dosed as part of Phase 1a dose escalation (24 in cabiralizumab monotherapy and 10 in cabiralizumab + nivolumab combination therapy) and 195 subjects have been dosed as part of Phase 1b dose expansion as of 1 August 2017. In Phase 1a, CK was elevated in 11 of 34 subjects (32%), and 3 events (1%) were Grade 3 or higher. AST was elevated in 16 of 34 subjects (47%), and 10 events (29%) were Grade 3 or higher. ALT was elevated in 4 of 34 subjects (17%), and none of these were Grade 3 or higher. In Phase 1b, CK was elevated in 82 of 195 subjects (42%), and 29 events (15%) were Grade 3 or higher. AST was elevated in 76 of 195 subjects (39%), and 14 events (7%) were Grade 3 or higher. ALT was

elevated in 39 of 195 subjects (20%), and five events (3%) were Grade 3 or higher. The serum enzyme elevations for Studies FPA008-001 and FPA008-002 follow a similar pattern.

Please refer to the cabiralizumab IB for more detailed information about these serum enzyme elevations.

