9. Willingness to provide an archival specimen block, if available, for research.

10. Patients must have normal organ and marrow function as defined below:

System	Laboratory Value
Hematological	
Absolute neutrophil count (ANC)	$\geq 1,500 / \mu\text{L}$
Platelets	$\geq 100,000 / \mu\text{L}$
Hemoglobin	$\geq 9 \text{ g/dL}$ or $\geq 5.6 \text{ mmol/L}$ without transfusion or EPO dependency (within 7 days of assessment)
Renal	
Serum creatinine OR Measured or calculated ^a creatinine clearance (GFR can also be used in place of	$\leq 1.5 \times$ upper limit of normal (ULN) OR $\geq 50 \text{ mL/min}$ for subject with creatinine levels $> 1.5 \times$ institutional ULN

creatinine or CrCl)	
Hepatic	
Serum total bilirubin	$\leq 1.5 \times \text{ULN}$ OR Direct bilirubin $\leq \text{ULN}$ for subjects with total bilirubin levels $> 1.5 \text{ ULN}$
AST (SGOT) and ALT (SGPT)	$\leq 2.5 \times \text{ULN}$
Albumin	$\geq 2.5 \text{ mg/dL}$
Coagulation	
International Normalized Ratio (INR) or Prothrombin Time (PT)	$\leq 1.5 \times \text{ULN}$ unless subject is receiving anticoagulant therapy as long as PT or PTT is within therapeutic range of intended use of anticoagulants
Activated Partial Thromboplastin Time (aPTT)	$\leq 1.5 \times \text{ULN}$ unless subject is receiving anticoagulant therapy as long as PT or PTT is within therapeutic range of intended use of anticoagulants

^aCreatinine clearance should be calculated per institutional standard.

11. Female subject of childbearing potential should have a negative urine or serum pregnancy within 24 hours prior to receiving the first dose of study medication. If the urine test is positive or cannot be confirmed as negative, a serum pregnancy test will be required.
12. Female subjects of childbearing potential should be willing to use a highly effective contraception (hormonal or IUD) or be surgically sterile, or abstain from heterosexual activity for a period of at least 5 months after the last dose of study drug. Subjects of childbearing potential are those who have not been surgically sterilized or have not been free from menses for > 1 year.
13. Male subjects should agree to use an adequate method of contraception starting with the first dose of study therapy through at least 7 months after the last dose of study drug.
14. Patients must have at least one measurable lesion at baseline by computed tomography (CT) or magnetic resonance imaging (MRI) as per RECIST v1.1 criteria.

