4.9 Criteria for Holding, Discontinuing, or Modifying Study Drug

Management of suspected adverse drug reactions may require temporary treatment hold (until re-treatment criteria are met), reducing the dose of APX005M, or discontinuation of some or all investigational products as per Table 5. If a subject experiences several toxicities, the recommended dose modification should be based on the highest grade toxicity.

Up to two dose reductions are permitted for APX005M. There are no dose reductions for cabiralizumab or nivolumab.

Table 5: Criteria for Holding, Discontinuing, or Modifying Study Drug

	Toxicity	Grade	APX005M	Cabiralizumab	Nivolumab
Gastrointestinal AEs	Diarrhea/colitis	2-3	1 st occurrence: Hold	Hold	Hold
			2 nd occurrence: dose reduction [¥]	If not improving in 28 days with oral steroids: Discontinue	If not improving in 28 days with oral steroids: Discontinue
	Vomiting	4	Discontinue	Discontinue	Discontinue
Endocrine AEs	Hypophysitis/ Endocrinopathies	2-4	Hold only if clinically unstable	Hold only if clinically unstable	Hold only if clinically unstable

	Toxicity	Grade	APX005M	Cabirizumab	Nivolumab
	Hyperthyroidism	2-4	Hold only if clinically unstable	Hold only if clinically unstable	Hold only if clinically unstable
Hepatic AEs	Increased AST/ALT	3 (> 5 to ≤ 12x ULN) and bilirubin <2x ULN	Continue	Continue	Continue
		3 (> 12x ULN) for >14 days and not decreasing on steroids and bilirubin <2x ULN	Hold	Hold	Hold
		2-3 and total bilirubin >2x ULN or 3x baseline for patients with Gilbert's syndrome and no cholestasis or INR >1.5 not on warfarin	Discontinue	Discontinue	Discontinue
		4	Discontinue	Discontinue	Discontinue
Increased bilirubin	Increased bilirubin	2	Hold	Hold	Hold
		3	Hold If >48 hours with no cholestasis or > 5 days with cholestasis: Discontinue	If >48 hours with no cholestasis or > 5 days with cholestasis: Discontinue	If >48 hours with no cholestasis or > 5 days with cholestasis: Discontinue
		4	Discontinue	Discontinue	Discontinue

	Toxicity	Grade	APX005M	Cabiralizumab	Nivolumab
Skin AEs	Rash or other skin toxicity	3	Hold If not improving in 28 days: Discontinue	Hold If not improving in 28 days: Discontinue	Hold If not improving in 28 days: Discontinue
		4	Hold If not improving in 28 days: Discontinue	Hold If not improving in 28 days: Discontinue	Discontinue
Neurological AEs	Neurological Toxicity	2	Continue	Continue	Hold
		3	Hold	Hold	1 st occurrence: Hold 2 nd occurrence: Discontinue
		4	Hold	Hold	Discontinue

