6.7 Potential Drug Induced Liver Injury

Wherever possible, timely confirmation of initial liver-related laboratory abnormalities should occur prior to the reporting of a potential drug-induced liver injury (DILI) event. All occurrences of potential DILIs, meeting the defined criteria, must be reported as SAEs.

Potential drug induced liver injury is defined as:

1. ALT or AST elevation $>3x$ ULN
and
2. Total bilirubin $>2x$ ULN ($> 2x$ baseline in patients with Gilbert's syndrome) without initial findings of cholestasis (elevated serum alkaline phosphatase) ***or*** INR $> 1.5 \times$ ULN (in the absence of anticoagulation)
and
3. No other immediately apparent possible causes of aminotransferase elevation and

hyperbilirubinemia including, but not limited to viral hepatitis, pre-existing chronic or acute liver disease, or the administration of other drugs known to be hepatotoxic.

7. Statistical Considerations

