Chemistry includes CK (creatinine kinase), AST (aspartate transaminase), ALT (alanine transaminase), alkaline phosphatase, bicarbonate, bilirubin, (direct and total), BUN (blood urea nitrogen), calcium, chloride, creatinine, glucose, LDH (lactate dehydrogenase), phosphorus, potassium, sodium, and, if applicable, serum pregnancy. Albumin, amylase, lipase, thyroid panel includes TSH, Free T4, PT/INR, and PTT (aPTT) perform at Screening and as indicated. If CK elevation is clinically significant, obtain troponins (cardiac and skeletal), CK isoenzymes, aldolase, and ECG; repeat CK and these additional tests within 48 hours or other interval as clinically indicated, until resolved or stable. If either AST or ALT is elevated, obtain total serum bilirubin, alkaline phosphatase; repeat within 48 hours or other interval, as clinically indicated, until resolved or stable. Additional tests may be obtained at any time, if clinically indicated.

Urinalysis: Urine dipstick will only be done at screening, and when clinically indicated.

- i. Obtain ECG records at Screening and the Day 28 post last infusion End-of-Treatment Visit. Additional ECGs should be obtained at any time, if serum CK or cardiac troponin is elevated; if abnormal (excluding sinus tachycardia), ECGs should be obtained (if clinically indicated), until the abnormality is resolved or clinically stable. Additional ECGs may be obtained at any time, if clinically indicated. ECGs for each patient should be obtained from the same machine whenever possible. To minimize variability, it is important that patients be in a resting position for at least 5 minutes prior to each ECG evaluation. Body position should be consistently maintained for each ECG evaluation to prevent changes in heart rate. Environmental distractions (e.g., television, radio, conversation) should be avoided during the pre-ECG resting period and during ECG recording.

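### DLT item 6 and Table 5 use an absolute INR above 1.5 and exempt only warfarin, so an eligible patient can already meet the INR limb at entry, and INR is not rechecked when AST/ALT rises

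*Combined protocol and SAP*

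**What the plan says.** Four rules bear on INR.

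- **Eligibility.** Section 3.2.2, criterion 10, sets INR or PT at no more than 1.5 x ULN, "unless subject is receiving anticoagulant therapy as long as PT or PTT is within therapeutic range of intended use of anticoagulants".
- **DLT.** Section 3.1.2.1.1, item 6, pairs Grade 3 or higher AST/ALT with a bilirubin limb "or INR > 1.5 not on warfarin".
- **Dosing.** The combined AST/ALT row of Table 5 (section 4.9) discontinues all three drugs at Grade 2-3 with raised bilirubin "and no cholestasis or INR >1.5 not on warfarin". DLT item 10 makes a DLT of "Any toxicity requiring dose reduction of APX005M or permanent discontinuation of any of the study drugs".
- **SAE reporting.** Section 6.7 defines potential drug-induced liver injury with INR above 1.5 x ULN, "in the absence of anticoagulation".

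The Table 5 Continue row (AST/ALT above 5 and up to 12 x ULN) and the AST/ALT exception in section 4.7 test bilirubin only. Neither mentions INR.

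On timing, note h of Appendix A lists "PT/INR, and PTT (aPTT) perform at Screening and as indicated". Its reflex rule is: "If either AST or ALT is elevated, obtain total serum bilirubin, alkaline phosphatase". Note h of Appendix B says the same. INR is not among the reflex tests.

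Section 1.4 describes AST elevation as a common finding with cabiralizumab and treats it as a pharmacodynamic marker.

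**The concern.** The INR limb exists to pick out an enzyme rise that comes with impaired liver function. It can do that only if the INR is abnormal because of treatment. Here the trigger is an absolute value with a narrow exemption, while the entry limit is relative to ULN with a wide one. A patient whom the protocol chose to admit may therefore carry a positive INR limb from screening. What is then new on treatment is only the enzyme effect that the protocol expects.

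In a 3+3 design this matters because each cohort has three to six patients. Under Table 3, one added DLT turns 0/3 into 1/3 and brings in three more patients; a second stops enrollment at that dose. Table 5 also governs Phase 1b, so an avoidable permanent discontinuation is not confined to escalation.

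The problem runs the other way too. With no INR required when AST/ALT rises, a real on-treatment INR increase may go unmeasured. If it is measured, the Continue row does not take it into account.

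**Working it through.** **1. The plan's AST figures.** Section 1.4.1, Phase 1b: "AST was elevated in 76 of 195 subjects (39%), and 14 events (7%) were Grade 3 or higher". Check: 76/195 = 39.0% and 14/195 = 7.2%. Phase 1a: 16/34 = 47.1% any grade and 10/34 = 29.4% Grade 3 or higher. Section 1.3.6.1.3.3 counts only cabiralizumab-related Phase 1b events: 65/195 = 33.3% any grade, and 10 Grade 3 AST events, 10/195 = 5.1%. The stated percentages reproduce.

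**2. INR overlap without an anticoagulant.** Entry cap = 1.5 x ULN; trigger = above 1.5; overlap = 1.5 x ULN - 1.5. The documents give no INR ULN, so the values below are assumed.

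| INR ULN | Entry cap | Overlap now | Overlap with trigger at 1.5 x ULN |
|---|---|---|---|
| 1.0 | 1.50 | 0 | 0 |
| 1.1 | 1.65 | 0.15 | 0 |
| 1.2 | 1.80 | 0.30 | 0 |

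**3. INR overlap on a non-warfarin anticoagulant.** Criterion 10 waives the cap; item 6 and Table 5 do not exempt the patient. This route needs no ULN, only the assumption that the drug takes INR above 1.5. Neither the exclusion criteria (3.2.3) nor the prohibited treatments (3.3.1) bar such drugs.

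**4. Two readings of the Table 5 combined row.**
- Reading A: (raised bilirubin and no cholestasis) or INR above 1.5. This matches item 6 and the emphasised alternative in 6.7.
- Reading B: raised bilirubin and (no cholestasis or INR above 1.5).

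**5. A worked patient.** AST is 6 x ULN for no more than 7 days (6 x 36 = 216 at the ULN of 36 used in item 5) and bilirubin is 1.0 x ULN. There is no anticoagulant, the assumed INR ULN is 1.1, and INR is unchanged since entry. Items 5a and 5b are not met.

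| Rule | INR 1.6 | INR 1.4 |
|---|---|---|
| Criterion 10 (cap 1.65) | eligible | eligible |
| DLT item 5c (longer than 1 week) | not met | not met |
| DLT item 6 | met | not met |
| Table 5 Continue row | met | met |
| Table 5 combined row, reading A | met: discontinue all three | not met |
| Table 5 combined row, reading B | not met | not met |
| 4.7 AST/ALT exception | next cycle allowed | next cycle allowed |
| 6.7 INR limb (above 1.65) | not met | not met |

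On reading A, Continue and Discontinue apply together. The section 4.9 tie-break goes by the highest-grade toxicity, but this is one toxicity at one grade, so it does not decide.

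**6. The same patient at Grade 2.** Grade 2 starts above 3 x 36 = 108 and Grade 3 above 5 x 36 = 180. At AST 4 x ULN (144), item 6 does not apply. On reading A, the combined row is the only AST/ALT row that fits, and item 10 then makes the discontinuation a DLT. On reading B, no AST/ALT row fits.

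**7. Which INR is used.** Screening is the only fixed time point. Unless the investigator orders another, the INR on file is the one that eligibility allowed.

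**The case against.** The strongest reply has four parts.

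*Both routes rest on facts outside the documents.* At an INR ULN of 1.0 the first route vanishes. The second needs a drug that raises INR above 1.5, and criterion 10 ties its waiver to a PT or PTT therapeutic range, which some anticoagulants may not have. This stands: the gap is conditional.

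*The DLT is not automatic.* Section 3.1.2.1.1 leaves out events clearly due to another cause, section 6 defines an adverse event as new or worsening, and the safety teleconference in 3.1.2.1 reviews concomitant medication and chemistry before each new or expanded dose level. A reader might infer that every such patient must be scored as a DLT; the documents do not go that far. But the new event is the AST/ALT rise, which is attributed to cabiralizumab. INR is only a qualifier, and no rule says a baseline INR is to be disregarded. The review can correct the count, but nothing written directs it to.

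*Table 5 need not contradict itself.* Reading B removes both the Grade 3 conflict and the Grade 2 route. The related Grade 2 or higher guidance in 4.8 requires raised bilirubin and has no INR limb, and 4.9 says only that reactions may require the tabled action. A reader might call the contradiction certain; it holds only on reading A. That reading is better supported by item 6 and 6.7, but the row is ambiguous. Item 6 is unaffected.

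*The AST figures overstate the effect.* Grade 3 elevations lasting more than a week are already DLTs under item 5c, so only shorter ones are added by the INR limb. The 7% and 29% also count events, come from treatment without APX005M, and are not limited to 28 days. A reader might turn them into a probability that a cohort expands; the documents do not support that step.

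**Conclusion.** The INR limb of the DLT and dosing rules does not match the INR that eligibility admits, or the protocol's own liver-injury definition. This is certain from the text. Whether it catches a patient depends on an INR ULN above 1.0 or a non-warfarin anticoagulant that raises INR above 1.5. Where it does, a Grade 3 or higher AST/ALT rise can be counted as a DLT under item 6 unless the safety review attributes it otherwise. Permanent discontinuation of all three drugs, including at Grade 2, follows only on reading A of the Table 5 row.

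No rate of affected patients can be given. The Grade 3 AST figures (about 5% to 29%) are upper-end context for how often the enzyme limb might follow, not an estimate of added DLTs. The lack of reflex INR testing needs neither assumption: a true on-treatment rise can be missed in any patient.

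A reader might also object that the hepatic rules use different baseline multiples for Gilbert's syndrome. That is not part of this point. DLT, SAE and dosing rules need not share a threshold, and sections 4.7 and 4.11 and the Grade 2 bilirubin hold limit redosing.

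**What to change.** 1. In DLT item 6 and the Table 5 combined row, replace the INR limb with INR above 1.5 x ULN "in the absence of anticoagulation", as in 6.7. For anticoagulated patients, preferably keep a limb: a rise over baseline INR not explained by the anticoagulant. This is narrower than dropping INR for all of them, in a combination not given before.
2. Punctuate the Table 5 row so that the INR limb is clearly separate from the bilirubin and cholestasis limb.
3. Add a condition that the INR limb is not met to the Continue row and to the AST/ALT exception in 4.7.
4. Add PT/INR to the reflex tests for raised AST/ALT in note h of Appendices A and B, so that the limb is judged on an on-treatment value.

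The cost is amendment wording and one PT/INR on a draw already triggered, with no new patients. The trade-off is a less sensitive INR limb in patients on non-warfarin anticoagulants and, where ULN exceeds 1.0, a slightly higher trigger for everyone else; the bilirubin limb and section 4.11 still apply. One small gap remains: criterion 10 accepts INR or PT, so a patient qualified on PT alone could still enter with INR above 1.5 x ULN.
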